#### **Visit Schedule**

Visit 1, Screening Visit: Previously described initial evaluation.

Visits 2: The occupational therapist will take circumferential and length measurements and/or 3D scan of the subject's arm and hand. These measurements/scan will be sent via encrypted email to the Maker Space, NYU Tandon School of Engineering, where the prosthesis will be fabricated using a 3D printer. As a secondary outcome measure, all subjects and their parents will be asked to complete the Pediatric Quality of Life Inventory (PedsQL).

Visits 3-4: The prosthesis will have been shipped or delivered to the occupational therapist who will use these two visits to adjust the prosthesis to optimize fit and functioning.

Visits 5-12: Occupational therapy treatment 1x week for 8 weeks. Each occupational therapy treatment will be a one-hour standardized session that will include the following: stretching/strengthening (approximately 20 minutes), bimanual training (approximately 20 minutes), and activities of daily living (approximately 20 minutes).

Visit 13 (one week after 8th occupational therapy treatment): Re-evaluation including measurement of upper extremity range of passive and active motion, level of spasticity/abnormal tone, MACS, AHA, Melbourne Assessment of Unilateral Upper Limb Function, PMAL, and PedsQL. These will be performed both with the prosthesis on and with it off.

Visit 14 (6 months after initiation of occupational therapy treatment): Re-evaluation including same assessments as Visit 13. These will be performed both with the prosthesis on and off.

Additionally, subjects will be asked to keep a log of daily activities including how long prosthesis is worn.

#### **Data Analysis and Data Monitoring**

Demographics will be reported. Passive and active range of motion measurements and the MACS, AHA, Melbourne Assessment, PMAL and the PedsQL scores at initial evaluation, end of occupational therapy treatment and 6 months follow-up will be compared. DSMP has been uploaded.

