**PURPOSE OF STUDY AND BACKGROUND**

**Purpose of the Study:** To assess the effectiveness of upper extremity prosthesis in improving the upper extremity function of children with cerebral palsy who have limited use of their hands

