A systematic review and meta-analysis was recently performed on the use of orthotics, or splints, in children with cerebral palsy. Unlike constraint or bimanual therapies, orthotics can be applicable to lower-functioning patients. When looking only at functional, as opposed to non-functional, hand splints, preliminary data showed a small, immediate benefit. Some investigators likened functional hand splints to being utilized like spectacles for vision, with the improved use present only during wear, while others speculated that the gains made during usage would carry over into times without wear. Currently, insufficient data exists to determine which theory is most accurate.

**Study Design:** Prospective one group pretest-posttest design

Primary outcome measures: passive and active range of motion, MACS, Assisting Hand Assessment, Melbourne Assessment of Unilateral Upper Limb Function, Pediatric Motor Activity Log  
Secondary outcome measure: Pediatric Quality of Life Inventory

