### **CHARACTERISTICS OF THE RESEARCH POPULATION**

**Number of Subjects:** Participants will be 12 children.

**Gender of Subjects:** Males and females will be enrolled

**Age of Subjects:** 4-17 years

**Racial and Ethnic Origins:** Participants of all racial and ethnic origins will be included.

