All visits for this study are for research purposes. The patient will be scheduled for Visit 1, Screening Visit. At Visit 1, a pediatric occupational therapist will perform a comprehensive initial evaluation to determine functional level, range of passive and active upper extremity motion, presence of contractures, and level of spasticity/abnormal tone. The evaluation will include the following widely used measures of upper extremity function in patients with cerebral palsy: MACS, the Assisting Hand Assessment (AHA), Melbourne Assessment of Unilateral Upper Limb Function, and Pediatric Motor Activity Log (PMAL). From this information the occupational therapist will determine patient's eligibility for enrollment, i.e., if the patient meets inclusion and exclusion criteria. Additionally, for the patients that are enrolled in the study, this will serve as their initial evaluation.

Those patients determined to be eligible and signed consent/assent/authorization forms will be fitted with a three-dimensionally printed arm prosthesis, which uses wrist or elbow tenodesis for grasp and release. Three-dimensional printers can manufacture prostheses, which use proximal motion to activate opening and closing of the fingers.

Patients with MACS III have limited active finger and wrist motion. Many patients with MACS level IV have a small amount of active wrist motion and minimal finger motion. These two groups of patients can have prostheses with extension caps on the fingers and thumb driven by wrist motion. The palmar fingertips would then be utilized for sensory input and additional fine control. In contrast, those patients (some MACS IV and some MACS V) with unusable, contracted fingers and no wrist motion may need more involved prostheses. Similar to prostheses for children with congenital finger amputations, a prosthetic hand component would be fitted over the existing hand, and extension and flexion of the prosthetic fingers (not just caps) would be driven by elbow motion.

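### The only comparison the protocol states is change over time in one group given prosthesis plus therapy, which does not isolate the prosthesis; on/off assessments are scheduled, but no on/off contrast is stated

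*Protocol*

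**What the plan says.** The Purpose of the Study is "To assess the effectiveness of upper extremity prosthesis in improving the upper extremity function of children with cerebral palsy" whose hand use is restricted. The Study Design line in Background gives the design as a "Prospective one group pretest-posttest design", and Number of Subjects says "Participants will be 12 children".

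Under Visit Schedule, the device is fitted at Visits 3-4. Visits 5-12 are eight weekly one-hour therapy sessions, split about equally between stretching/strengthening, bimanual training and activities of daily living. Visits 13 and 14 repeat the assessments, each time with the prosthesis on and with it off.

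Data Analysis and Data Monitoring lists range of motion, MACS, AHA, Melbourne, PMAL and "PedsQL scores at initial evaluation, end of occupational therapy treatment and 6 months follow-up will be compared". It does not mention the on and off conditions, and no other section does so in connection with analysis.

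Background reports two views of functional splints: "with the improved use present only during wear, while others speculated that the gains made during usage would carry over into times without wear". It then adds "Currently, insufficient data exists to determine which theory is most accurate".

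**The concern.** The aim concerns the device. The stated comparison concerns everything that happens to a child between the initial evaluation and the two re-evaluations. One of those things is bimanual training, which Background lists among the techniques with the most supportive evidence. Therapy is therefore a credible rival explanation on the protocol's own account. Growth in children aged 4-17 and familiarity with repeated tests add to it.

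At stake is what the trial can report. A gain over time could be read as effectiveness of the prosthesis when it cannot be assigned to the prosthesis. Meanwhile, the scores that bear most directly on benefit during wear have no stated use, although the children will be tested twice at each re-evaluation to obtain them.

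**Working it through.** The protocol gives no effect size, SD, alpha or power, so there is no figure of its own to reproduce. The check is mainly structural.

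**What each comparison contains.** Suppose effects add up, and define:
- B: the device's effect on scores when it is worn.
- c: the share of B that persists when it is off (carry-over).
- T, G, R: the effects of therapy, growth and retesting.

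The initial evaluation precedes fabrication, so the baseline is always without the device.

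| Comparison | Content |
|---|---|
| Visit 13 on, minus baseline | B + T + G + R |
| Visit 13 off, minus baseline | cB + T + G + R |
| Visit 13 on, minus Visit 13 off | (1 - c)B |

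Three things follow.

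1. T + G + R is in both over-time comparisons. Choosing the on or the off score does not remove it.
2. The same-visit difference removes T + G + R, because age, date and therapy received are the same for both scores. This holds for exposure to therapy. If sessions after fitting trained the child to use the device, therapy acts more on the on score and a training term is added to (1 - c)B.
3. At each visit there are two independent equations and three unknowns: B, c and T + G + R. On-minus-off therefore estimates benefit while worn, not total benefit, and carry-over makes it smaller. The one-group design cannot separate carry-over from therapy, growth and retesting.

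**Test order.** Suppose the second test of the day is shifted by an amount o. If every child is tested in the same order, on-minus-off moves by the full o, up or down. With 6 children each way the mean shift is (6 x o - 6 x o)/12 = 0. Visit Schedule states no order.

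**Precision, assuming a 95% paired t interval and complete pairs.** The half-width in SDs of the within-child difference is t(n-1)/sqrt(n).
- n = 12: 2.201/3.464 = 0.635.
- n = 12 with test order in the model (10 degrees of freedom): 2.228/3.464 = 0.643.

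**By device design.** Methods and Procedures describes two devices. One type is "prostheses with extension caps on the fingers and thumb driven by wrist motion". In the other, "extension and flexion of the prosthetic fingers (not just caps) would be driven by elbow motion". The number of children per design is not given, so the sizes below are assumptions:
- n = 4: half-width 1.59 SD.
- n = 6: half-width 1.05 SD.
- n = 8: half-width 0.84 SD.

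Results by design can only be descriptive. Active range of motion needs that split, because with a prosthetic hand the finger motion seen with the device on is the device's own.

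**The case against.** **Analysis plan.** The analysis section is a short summary, and on/off contrasts are often specified in an analysis plan, which may exist and is not shown. Scheduling every assessment in both conditions suggests that a contrast was intended. This stands in part. A reader might infer that the pairs will not be contrasted, but the protocol says no such thing; it only states no contrast. What remains does not depend on an unseen plan. The comparison that the protocol does state cannot separate device from therapy, whichever score is entered. Test order is a matter of visit conduct, and a fixed order cannot be undone at analysis.

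**Disclosed design.** What over-time change cannot show is a property of the one-group design, which is stated openly. That stands, and the design is not faulted here. Risk also describes splinting as a usual part of therapy in these children, so assessing the two together is natural. That is a reason to label the result as belonging to the combined programme.

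**Partial answer.** On-minus-off leaves out carry-over, is seen by child and assessor alike, and may include training in device use. All of this stands. It is why the contrast belongs beside the over-time comparison and does not replace it, and why a small value would not show that the prosthesis failed.

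**A stronger reading.** A reader might infer that the plan carries an inflated rate of false claims of effectiveness. The protocol does not support a figure. It names no test, alpha or success criterion and says only that scores will be compared, and it gives no size for the effects of therapy, growth, retesting or test order.

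**Conclusion.** The point holds in a limited form. The stated comparison answers a question about the combined prosthesis-plus-therapy programme, while the purpose is worded as a question about the prosthesis. A better-matched contrast for benefit while worn can be made from assessments already scheduled, and none is stated.

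This rests on the text and on the assumption of additive effects, not on any assumed effect size. The only size given is the precision of the proposed contrast: about 0.64 SD of the within-child difference either side, under a paired t interval with all 12 children contributing. That is imprecise, and fewer complete pairs would make it worse.

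No statement in the protocol is shown to be false. This is a cheap improvement worth making before data are collected. Off-prosthesis change will remain unattributable to the device in any case.

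**What to change.** 1. **Data Analysis and Data Monitoring.** Add the within-child on-minus-off difference in AHA and Melbourne scores at Visit 13, repeated at Visit 14, as the estimate of benefit while worn. Keep the over-time comparison beside it. Report active range of motion on and off descriptively, by device design.
2. **Visit Schedule.** Balance the order of on and off testing, 6 children each way, or at least record the order used.
3. **Wording of the over-time results.** Say which condition's scores enter the comparison. Describe the change, including change in MACS, PMAL and PedsQL, as change after the combined prosthesis-plus-therapy programme and not as an effect of the device alone.
4. **Limits to state with the contrast.** It is unblinded, may include training in device use, does not capture carry-over (which would shrink it), and is imprecise with 12 children.

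The cost is a few sentences in the analysis section and one line on test order. No additional children, visits or measures are needed.

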#### **Data Storage and Confidentiality**

The data will be stored on a computer to which only research personnel have access and will be password protected to prevent unauthorized access. Data will be stored in either the locked office of the PI or the research coordinator.

#### **RISK/BENEFIT ASSESSMENT**

##### **Risk**

This study is low risk because it involves the fabrication and use of upper extremity splinting, which are commonly an integral part of typical occupational therapy treatment of this population of children. The primary difference will be in the fabrication technique, 3D printing, being utilized. For the evaluations, measurements, scans and treatment by the occupational therapists, the only potential for any discomfort would be mild discomfort during the stretching portion of the treatment session. For the prosthesis, one risk is minor skin irritation or discomfort from it.

##### **Protection Against Risks**

The parents and children will be instructed to monitor the upper extremity for redness or discomfort and report any problems to the occupational therapist.

All necessary precautions will be taken to maintain confidentiality of data and prevent unauthorized access to data. The data will be entered into a REDCap database. Only personnel associated with this study will have access to the data. The data will be stored and accessible only on password-protected computers.

##### **Potential Benefits to Subjects**

The use of the prosthesis may improve the subject's upper extremity function.

#### **INVESTIGATOR'S QUALIFICATIONS & EXPERIENCE**

All research personnel have completed the CITI tutorial training in the protection of human subjects. Copies of the CVs of all personnel are included.

## **SUBJECT IDENTIFICATION, RECRUITMENT AND CONSENT/ASSENT**

### **Method of Subject Identification and Recruitment**

Subjects will be patients, aged 4-17 years, with diagnosis of cerebral palsy and MACS level III - V who have been seen at regular clinic/office/occupational therapy visit by PI, co-investigators or occupational therapist and indicated as a potential subject for study. Each subject will be scheduled for Visit 1, Screening Visit, with a pediatric occupational therapist who will perform a comprehensive evaluation.

Additionally, the PI, co-investigator and occupational therapists will review their own individual databases for potential subjects and contact them by phone to describe the research project. Telephone Recruitment Transcript has been uploaded. If patient and parent are interested, then the patient will be referred to the occupational therapist. For these subjects, the occupational therapist or research coordinator will be obtaining consent/assent (please see Process of Consent section below for further details) when the patient comes for Visit 1, Screening Visit.

For all subjects, from the information acquired through this Visit 1 evaluation, the occupational therapist will determine who is an appropriate candidate for inclusion in the study.

### **Process of Consent**

At a regular clinic/office/occupational therapy visit, potential participants and their parents/legal guardians will be approached by the PI, co-investigator, or occupational therapist who will describe the project to them. For non-English speaking participants, the institution's translation services, a health-care specific telephonic interpreting system, will be used to present the study information verbally and the Short Consent Form in the parent's native language will be used to obtain signed consent.

If the parent/legal guardian and child are interested, the Consent Form and age appropriate Assent Form will be presented by the PI, co-investigator, occupational therapist, or research coordinator. For those patients recruited from the databases of the PI, co-investigator or occupational therapist, the Consent/Assent forms will be presented by the occupational therapist or research coordinator. The parent/legal guardian and patient will be given the opportunity to read the forms and ask and have thoroughly answered any questions that they may have. Only after the parent/legal guardian and child assure the presenter that they fully understand the project and voluntarily agree for the child to participate, will their signatures be obtained. Parents will be given copies of the signed Consent and Assent Forms. Signed Consent and Assent Forms will be stored in subjects' files/binders in a locked office.

**Subject Capacity:** A review of the patient's medical record as well as a discussion with parent/legal guardian will be used to assess the patient's ability to provide assent and sign the form. If unable to sign and patient is able to indicate an understanding of the study, verbal assent will be obtained. Additionally, children without the capacity to provide assent will be included because they may benefit from this study in that their upper extremity function might improve.

### **Costs to the Subject**

No costs will be incurred by the subject or his/her family.

### **Payments for Participation**

Transportation costs up to \$50 will be reimbursed for each completed visit. Participant will be required to provide a receipt of costs incurred in order to receive reimbursement.

